## **6.11 Safety Analyses**

All safety analyses will be conducted on the Safety Population. The evaluation of safety will be based primarily on the frequency of adverse events (AEs), clinical laboratory assessments (chemistry, hematology, and urinalysis), 12-lead electrocardiograms (ECG), physical examinations, weight, waist circumference, and vital signs (heart rate, blood pressures, respiratory rate, and temperature). Other safety data will be summarized as appropriate.

### **6.11.1 Adverse Events**

For the purposes of this study, any sign (including a clinically significant laboratory result) or medical diagnosis noted by medical personnel, or symptom reported by the subject, regardless of relationship to investigational drug, that is treatment-emergent is considered to be an AE. All adverse events reported by the subject or observed by study site personnel from time of informed consent until completion of the study or premature withdrawal must

be recorded in the subject's CRF as per the CRF instructions. All AEs will be coded using Medical Dictionary for Regulatory Activities (MedDRA).

Treatment-emergent adverse events (TEAEs) are defined as those AEs that have a start date on or after the first dose of study medication, or occur prior to the first dose and worsen in severity or relationship to study medication after the first dose. AEs beginning >7 days after last dose will not be considered treatment emergent. An overview of AEs will be provided by treatment group and in total for the following information:

- All TEAEs,
- Maximum severity of TEAEs,
- Study drug-related TEAEs,
- Maximum severity of drug-related TEAEs,
- All serious adverse events (SAEs),
- All treatment-emergent SAEs,
- Drug-related SAEs,
- Death due to AEs,
- Withdrawals due to AEs, and
- Withdrawals due to study drug-related AEs.

The numbers and percentages of subjects with TEAEs will be summarized for each treatment group and in total by MedDRA system organ class and preferred term. Similar summaries will be provided by maximum severity. Drug-related TEAEs will be summarized in the same manner. Listings of SAEs and AEs leading to study medication discontinuation will be provided.

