	
• HbA1c and the homeostatic model assessment of insulin resistance (HOMA-IR)• Serum lipid profile: total cholesterol, triglycerides, low density lipoprotein (LDL) and high density lipoprotein (HDL) fractions. 
Liver Function:
 
• Mean change from baseline in serum ALT at week 24.• Mean serum aspartate aminotransferase (AST), alanine aminotransferase (ALT), and gamma-glutamyl transpeptidase (GGT) at weeks 4, 8, 12, 16, 20, and 24.• Proportion of subjects whose ALT level at week 24 is within normal range defined as < 20 U/L for women and < 30 U/L for men.
Exploratory Outcome Measures:	
• Mean serum concentrations of lipopolysaccharide (LPS), c-reactive protein (CRP), cytokeratin (CK)-18 fragments, proinsulin c-peptide, glucagon-like polypeptide (GLP-1) and adiponectin.• Relative levels of inflammatory cytokines, interferon gamma (IFN-γ), and tumor necrosis factor alpha (TNF-α)• Relative levels of regulatory T cells in the peripheral blood mononuclear cells (PBMC) samples including CD4, CD8, CD 25, Fox P3, NKT, and CD62 T cells.
Methodology:	
Study design	Randomized double blind, placebo control 3-arm parallel group, multi-dose single center study
Study duration	Up to 28 days for screening, 24 weeks of treatment and 28 days of follow-up. Subjects terminating study drug will be followed-up post-treatment for 28 days.
Number of Subjects:	The study will aim to recruit 60 subjects, randomized 1:1:1
Stratification:	Treatment allocation will be stratified by known diagnosis of diabetes status. Nondiabetic status will be defined as HbA1c \leq 6.0 and absence of any medications to treat diabetes. Diabetic status will be defined as HbA1c $>$ 6.0 and/or requiring medication for treatment of diabetes mellitus.
Study Drug:	JKB-121 oral tablet
Control Group	Placebo to match
Dose Regimens	Arm A: 5 mg JKB-121 twice daily. Arm B: 10 mg JKB-121 twice daily Arm C: Matching placebo twice daily All treatment dose regimens are administered per orally
Administration: Schedule:	Twice daily for 24 weeks

Study Population:	Adults with biopsy-proven nonalcoholic steatohepatitis (NASH)

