6.1 Duration of the Study

Subjects will be on treatment for up to 24 weeks. Subjects who experience adverse reaction will discontinue study drug but will continue to complete all protocol-specified follow-up visits, assessments and evaluations. They will then continue to be followed up for the remaining duration of the study. Unless otherwise recommended by the Independent Data Review Board (IDRB) or regulatory authorities, the study will continue until it accrues a minimum of 60 subjects complete the study.

Until formal conclusion of the study, subjects, investigators and all site study personnel will be remain blinded as to treatment allocation, except in the event of a medical emergency which necessitates unblinding.

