12. ADVERSE EVENTS: DEFINITIONS AND MANAGEMENT

At the time of written informed consent, the subject must be given the name and telephone number of personnel at the study site who can be contacted in the event of an emergency or to report any medical symptom or untoward medical occurrence that is of concern to the subject. Investigators will closely monitor the subject for adverse events.

All adverse events reported by the subject or observed by study site personnel from time of informed consent until completion of the study or premature withdrawal must be recorded in the subject's CRF as per the CRF instructions. Adverse events are to be recorded regardless of relationship to study drug. Information to be recorded will include, but not be limited to, relationship of the event to study drug and severity of the event. These terms are defined in Sections 12.4.5.5 &12.4.5.6 below. Specific instructions for management of adverse events will be reviewed with study site personnel by the Clinical Monitor prior to study start.

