12.1.2 Adverse Events

For the purposes of this study, any sign (including a clinically significant laboratory result) or medical diagnosis noted by medical personnel, or symptom reported by the subject, regardless of relationship to investigational drug, that is treatment-emergent is considered to be an adverse event.

TaiwanJ Pharmaceuticals defines treatment-emergent are defined as follows:

- 1) Has onset any time after the start of investigational drug treatment OR
- 2) Has worsened since the event was previously reported (this includes worsening of signs, symptoms, abnormal laboratory values, or diagnoses that were present prior to the first dose of investigational drug but then worsened any time after the start of investigational drug treatment)

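### The SAP's 7-day limit on treatment-emergent AEs conflicts, without explanation, with the protocol's open-ended definition and leaves later non-serious AEs in no AE output the SAP names

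*SAP*

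**What the plan says.** **Definition.** Protocol 12.1.2 gives two routes to treatment-emergent status. The first is "Has onset any time after the start of investigational drug treatment"; the second is worsening after drug has started. Neither has an end date. SAP 6.11.1 repeats the protocol's general description of an AE, sets the same starting point, and then closes the window: "AEs beginning >7 days after last dose will not be considered treatment emergent". It gives no reason and does not flag a departure from the protocol.

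**Recording.** Under protocol Section 12, AEs "from time of informed consent until completion of the study or premature withdrawal must be recorded", and SAP 6.11.1 repeats this rule. Protocol 10.4.5 has AEs recorded at the Week 28 visit. Protocol 12.3.1 has SAEs reported up to 30 days after the last dose.

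**Follow-up.** The synopsis gives the study duration as "Up to 28 days for screening, 24 weeks of treatment and 28 days of follow-up". For subjects who stop drug early the protocol says different things. The synopsis states "Subjects terminating study drug will be followed-up post-treatment for 28 days", and 10.4.6 describes an end-of-treatment visit and a follow-up visit four weeks later. Section 6.1, on subjects who stop because of an adverse reaction, says "They will then continue to be followed up for the remaining duration of the study", and 10.1 asks for all evaluations whether or not the subject is still on drug.

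**Endpoint and outputs.** The synopsis makes AE incidence and severity part of the primary safety endpoint, with vital signs and laboratory tests. Protocol 13.4.3.1 lists the rates of patients with any AE, SAEs, AEs leading to discontinuation, and AEs by CTCAE grade. In SAP 6.11.1 the tables by system organ class and preferred term, by maximum severity and for drug-related events are all TEAE tables. The AE listings named are for SAEs and for AEs leading to discontinuation.

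**The concern.** The protocol has events collected through Week 28 and counts them as treatment-emergent. The SAP takes the same data and drops those that start late. A non-serious AE in that period, even one of Grade 3 or judged related to drug, has no place in the AE outputs the SAP names unless it leads to withdrawal.

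The affected quantities are the any-AE rate, the severity and grade summaries, and the drug-related summaries. They are how this trial reports a primary safety endpoint. Because the limit runs from each subject's last dose, the counted period also shortens for anyone who stops early, including those who stop because of an adverse reaction.

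**Working it through.** **Inputs.** End of treatment Day 168 ± 4 and follow-up visit Day 196 ± 4 (protocol 10.2.1). Post-treatment follow-up 28 days (synopsis). SAP limit 7 days after last dose (SAP 6.11.1). Assumption: a completer's last dose falls at the end-of-treatment visit.

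**Reproducing the plan's figure.** 28 × 7 − 24 × 7 = 196 − 168 = 28 days, as the synopsis states.

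**Completer.** Excluded share of off-drug time = (follow-up days − 7) / follow-up days.
- Nominal visits: (28 − 7)/28 = 21/28 = 75%.
- Shortest interval within the visit windows: 192 − 172 = 20 days, so 13/20 = 65%.
- Longest interval: 200 − 164 = 36 days, so 29/36 = 81%.
- Against all nominal time after first dose: 21/196 = 10.7%. The counted window is 168 + 7 = 175 days instead of 196.

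**Early stopper followed for 28 days (synopsis, 10.4.6).** 21/28 = 75%, the same as a completer.

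**Early stopper followed to Day 196 (6.1, 10.1).** Off-drug days = 196 − stop day; excluded days = off-drug days − 7.

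| Last dose | Off-drug days | Excluded | Share of off-drug time | Share of 196 days |
|---|---|---|---|---|
| Day 28 | 168 | 161 | 96% | 82% |
| Day 84 | 112 | 105 | 94% | 54% |
| Day 140 | 56 | 49 | 88% | 25% |

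**Possible effect on the any-AE rate (illustration only).** The documents give no AE rates. Assume a constant hazard for a completer's first AE. A 196-day rate p then shows as 1 − (1 − p)^(175/196). Rates of 20%, 40%, 60% and 80% become 18.1%, 36.6%, 55.9% and 76.2%, a drop of about 2 to 4 percentage points. With 20 subjects per arm, one subject is 1/20 = 5 points.

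**Which components are cut (SAP 6.11.1 to 6.11.3).**
- Cut: TEAEs by system organ class and preferred term, TEAEs by maximum severity, drug-related TEAEs, and the treatment-emergent SAE row.
- Not cut: the row for all SAEs (separate from treatment-emergent SAEs), drug-related SAEs, deaths due to AEs, withdrawals due to AEs, and the two listings. None of these is restricted to TEAEs.
- Not cut: laboratory and vital-sign summaries, which cover all scheduled post-baseline visits. The worst-value laboratory tables run from first dose with no 7-day limit.

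**The case against.** A bounded on-treatment window is a legitimate analysis choice, because it keeps off-drug background events out of the comparison. The events most likely to matter are retained: SAEs, deaths and withdrawals have their own rows, and discontinuation AEs would normally start before the last dose. For a completer only 10.7% of time after first dose is lost, and under a constant hazard the any-AE rate moves by less than one subject per arm. SAP Section 7 places the table and listing mock-ups in a separate document, which may include a listing of all AEs, and SAP 6.11 allows other safety data to be summarised as appropriate.

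Much of this stands. A reader might infer that the whole primary safety endpoint loses three quarters of follow-up. The documents do not support that: several components are untouched, and 75% describes only the 28-day off-drug period. Nor can one say that late events will be reported nowhere, only that the SAP text commits to no output for them.

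The objection does not remove the conflict. A bounded window can be defended, but the SAP neither defends this one nor acknowledges that the protocol defines the term differently. The constant-hazard illustration covers completers only, not subjects who stop early and stay in follow-up.

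**Conclusion.** The point holds for non-serious AEs that start on day 8 or later after the last dose and do not lead to withdrawal. The any-AE, severity or grade, and drug-related summaries omit them, contrary to protocol 12.1.2. For a completer the loss is 75% of post-treatment follow-up (65% to 81% across visit windows) and 10.7% of all time after first dose, assuming the last dose is taken at the end-of-treatment visit.

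For early stoppers the size depends on protocol statements that do not agree: about 75% of off-drug time under the synopsis and 10.4.6, and 88% to 96% in the examples above under 6.1 and 10.1. Those statements need to be reconciled.

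A reader might go further and conclude that an arm with more early stopping will look safer than it is. That is only conditional. It requires follow-up beyond 28 days off drug, different stopping between arms, and late events that would change a subject's classification. The documents give no discontinuation or off-drug AE rates. If those conditions hold, such an arm has less counted AE time and could look safer. The AE that prompted the stop would still be counted.

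**What to change.** Before the blind is broken, make one of two changes to SAP 6.11.1.

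1. Use the protocol definition, onset or worsening from first dose through the last study visit, for the main TEAE tables. Show AEs starting within 7 days of last dose as a supplementary table. The last visit is not a limit stated in 12.1.2, but it matches the recording period in protocol Section 12.
2. Keep the 7-day window, state it as a departure from protocol 12.1.2 with a reason, and add a by-arm table and a listing of AEs starting more than 7 days after the last dose.

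Under either option, state how long AEs are counted for subjects who stop drug early, once the protocol's follow-up statements have been reconciled.

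The cost is a wording change and an extra table or listing, from data already collected. The downside of the first option is that some off-drug background events enter the main tables. Randomisation gives no guarantee that these are equal across arms of 20, which is why the within-7-days subset should be shown alongside.

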### **6.11.2 Clinical Laboratory Evaluations**

Summary statistics will be provided for safety laboratory tests at baseline and all scheduled post-baseline visits for chemistry, hematology, and urinalysis assessments by treatment group and in total. The change from baseline to post-baseline visits will also be presented.

The number and frequency of subjects with laboratory abnormalities (worst value post first dose for each subject) will be summarized by treatment group and in total. Shift tables from baseline to worst value post first dose will be presented for ALT and AST (>1xULN to ≤2xULN, >2xULN to ≤3xULN, >3xULN) and CK (>1xULN to ≤5xULN, >5xULN to ≤10xULN, >10xULN).

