Study Procedures and Visit Schedule:	
Refer to Table 1 for the schedule of study procedures.
 
Subjects who provide voluntary written informed consent will be screened for eligibility. Subjects meeting all the inclusion and none of the exclusion criteria will be eligible to participate.
 
The maximum time on study drug for each subject is 24 weeks with an additional 4 weeks of follow-up.
 
Eligible subjects will be randomized at the baseline visit to receive one of three study treatments twice daily for a period of 24 weeks. Each subject will return for assessment and required study procedures on days 14, 28 and every 4 weeks thereafter until week 24. A final follow-up visit will be conducted at week 28 if the subject ceases treatment at week 24.
 
Investigational product dispensing and accounting will be conducted on a 4 week basis.
 
The actual visit schedule will be as follows:
 
• Screening period, culminating in randomization (screening assessments must be completed no more than 4 weeks prior to enrollment).• Baseline visit and every 4 weeks afterward for total of 24 weeks• Week 8, 16 and 24 (\pm 4 days) visits will include measure of metabolic (glucose, lipids, glycosylated hemoglobin, HOMA-IR, C-reactive protein etc.)• Week 12 and 24 (\pm 4 days) will include measures of hepatic steatosis and exploratory measures (i.e. CK-18, adiponectin, leptin, ghrelin, TNF-α, TGF-β, hyaluronic acid, cytokines, and MMP-2 etc)• Follow-up visit at week 28 (\pm 4 days).• Unscheduled or early withdrawal visits may be necessary.
Safety Assessment	
Safety Parameters:	
The following measures of safety and tolerability will be conducted at screening, baseline and every 4 weeks during the study:
 
• Adverse event monitoring• Physical examination including vital signs• Safety laboratory assessments• Treatment compliance• Urine pregnancy test (women only) 
The following measures of safety and tolerability will be conducted at screening, baseline and every 12 weeks during the study:
 
• Electrocardiogram (EKG)• Urinalysis

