8.1. Subject Inclusion Criteria

Subjects must meet all of the following inclusion criteria to be eligible for enrollment into the study:

1. Age \geq 18 years
2. Provision of written informed consent
3. Biopsy-proven NASH within 12 months prior to randomization as reviewed by central pathologist with:
 - NASH activity score (NAS) of 4 or more
 - 10% or more macrovesicular steatosis
 - cytologic ballooning score of at least 1 point
 - hepatic fibrosis of at least 1 point
 - hematoxylin and eosin (H&E) stained slides and/or paraffin block available for independent assessment
4. ALT $>$ 40 U/L for women and $>$ 60 U/L for men at screening and at least once in the previous 12 months.
5. MRI with $>$ 6% hepatic steatosis
6. HbA1c of \leq 9.0
7. Lipid lowering agents (i.e. statins) and allowable antidiabetic treatment (i.e. metformin or sulfonylurea) must be stable at screening and during the study.
8. Agree to use of effective contraceptive measures if female of child bearing potential.

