13.4.3.2. Other Safety Endpoints

Change from Baseline for each interval-valued laboratory test, vital signs, and other safety related variables will be summarized regarding each scheduled visit. Shift tables will be presented for laboratory values based on the central laboratory normal ranges.

All abnormalities deemed clinically significant by the investigator will be presented in detail and listed by patient identifier. The patients who have no laboratory results at the Screening or post-Baseline visit will be excluded from the change from Baseline and shift table analyses. Treatment effect will be explored by inspection of observed means or rates for the dose groups within each treatment regimen.

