### **6.11.3 Vital Signs and ECG**

Height, weight, waist circumference, and vital signs will be summarized at baseline and each scheduled post-baseline visit. The change from baseline will also be presented.

The overall ECG interpretation will be summarized by scheduled visit with counts and percentages by treatment group and in total.

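### The laboratory-abnormality count and the ECG table ignore baseline, and the SAP narrows the protocol's shift tables to three analytes

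*SAP*

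**What the plan says.** **Laboratory count.** SAP 6.11.2 plans: "The number and frequency of subjects with laboratory abnormalities (worst value post first dose for each subject) will be summarized by treatment group". Neither a baseline condition nor a definition of abnormality is given.

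**Shift tables.** The same section continues: "Shift tables from baseline to worst value post first dose will be presented for ALT and AST", and adds CK. No other analyte is named. Protocol 13.4.3.2 is wider: "Shift tables will be presented for laboratory values based on the central laboratory normal ranges". The efficacy and safety part of the protocol synopsis makes the same general commitment. The SAP gives no reason for the narrower list.

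**Change from baseline.** For chemistry, haematology and urinalysis, SAP 6.11.2 also says: "The change from baseline to post-baseline visits will also be presented".

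**ECG.** SAP 6.11.3 plans: "The overall ECG interpretation will be summarized by scheduled visit with counts and percentages by treatment group and in total". A pre-dose tracing exists: the protocol synopsis lists the ECG among measures "conducted at screening, baseline and every 12 weeks during the study", and Protocol 10.3.2 includes it at screening.

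**Entry.** Protocol 8.1 requires "ALT $>$ 40 U/L for women and $>$ 60 U/L for men at screening and at least once in the previous 12 months" and allows HbA1c up to 9.0. Protocol 12.4 states that every patient will have raised liver enzymes at baseline.

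**The concern.** A subject whose value was abnormal before the first tablet, and stays so, is counted in the laboratory-abnormality table in the same way as one who became abnormal on treatment. Where a test has a baseline-to-worst shift table, the reader can separate the two. Where it has none, the abnormality count is the only categorical summary of the measured values, and it cannot separate them. Glucose and GGT are the clearest cases: both are in the chemistry panel, neither has a direct entry limit, and this population gives reason to expect raised values.

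The ECG table has a related limit. At a given visit, one subject who becomes abnormal and one who returns to normal leave the arm's count unchanged, so the table does not show who changed.

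At stake is how readily a real difference in new abnormalities would be seen in arms of 20. The SAP already treats adverse events differently: under 6.11.1 a pre-dose event counts as treatment-emergent only if it worsens.

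**Working it through.** The documents give no abnormality rate and no figure for this table, so there is nothing to reproduce. The calculation below is an illustration on assumed rates.

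**Inputs**
- n = 20 per arm (SAP 6.1).
- b = share of subjects abnormal at baseline. Not in the documents; varied from 0 to 40%.
- q1 = 30% (dose) and q0 = 5% (placebo) = new abnormality among subjects normal at baseline. Assumed.
- Subjects abnormal at baseline also have an abnormal worst post-dose value. Assumed.

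**Formulas**
- Planned table, expected proportion per arm: b + (1 − b)q.
- New abnormalities only, all subjects as denominator: (1 − b)q.
- Expected difference between arms, in either table: (1 − b)(q1 − q0). The term b cancels, so the planned table is not biased for this difference.
- Chance that the dose shows no more affected subjects than placebo: sum over k of P(X1 = k) × P(X0 ≥ k), with X1 and X0 independent binomials on 20 subjects.

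**Results**

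| b | Planned table, placebo v dose | New only, placebo v dose | Difference (points) | Chance dose ≤ placebo, planned v new only |
|---|---|---|---|---|
| 0 | 5.0% v 30.0% | 5.0% v 30.0% | 25.0 | 2% v 2% |
| 10% | 14.5% v 37.0% | 4.5% v 27.0% | 22.5 | 7% v 3% |
| 30% | 33.5% v 51.0% | 3.5% v 21.0% | 17.5 | 16% v 6% |
| 40% | 43.0% v 58.0% | 3.0% v 18.0% | 15.0 | 21% v 8% |

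**Worked line, b = 30%.** Planned: 0.30 + 0.70 × 0.05 = 0.335 and 0.30 + 0.70 × 0.30 = 0.510. The ratio is 1.52, against 6.0 for new abnormalities. The standard error of the difference is √[(0.335 × 0.665 + 0.510 × 0.490)/20] = 0.154, so difference/SE = 0.175/0.154 = 1.14. New only: √[(0.035 × 0.965 + 0.210 × 0.790)/20] = 0.100, so difference/SE = 1.75. The expected difference is the same; the noise around it is about half as large again in the planned table.

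**Share of the dose-arm count that is pre-existing,** b/[b + (1 − b)q1]: 27% at b = 10%, 59% at 30%, 69% at 40%.

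**Other assumed rates.** With q1 = 50% and q0 = 10%, at b = 30%, the chance is about 5% as planned against 2% for new abnormalities. The loss is smaller when the drug effect is larger.

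**Limit case.** At b = 100% the planned table reads 100% in both arms, and a normal-to-abnormal count reads zero in both. ALT is close to this. The entry floor exceeds both normal ranges used for efficacy in SAP 5.2 (below 20 U/L for women and 30 U/L for men, or below 40 U/L). The safety laboratory's own upper limit is not given. For such tests only worsening from baseline is informative.

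**The case against.** Much of the opposing case stands.

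- **The safety assessment does not rest on this table.** A reader might infer that the primary safety assessment is compromised. The synopsis endpoint is changes in laboratory tests, and SAP 6.11.2 plans change from baseline for all of them. Protocol 13.4.3.1 lists only adverse-event rates as primary safety endpoints.
- **Some categorical output is conditioned on baseline.** Clinically significant laboratory results are recorded as adverse events and must be treatment-emergent to count. This covers only results the investigator judges significant, and mean changes can hide a few marked individual shifts, so neither replaces a baseline-conditioned count.
- **ALT and AST already have shift tables.** An abnormality row reading nearly 20 of 20 for ALT would be uninformative, but the next sentence of the SAP supplies the remedy for that analyte.
- **Entry criteria limit the problem.** Exclusion 19 sets limits for bilirubin, INR, albumin, creatinine, haemoglobin, platelets and neutrophils. That an abnormal value is permitted does not show that it is common.
- **Abnormality is undefined.** Table mock-ups are in a separate document (SAP 7). A threshold such as a multiple of the upper limit would reduce the mixing.
- **ECG.** If the by-visit table includes screening, arm-level comparison with the pre-dose state is possible. The protocol does not promise an ECG shift table, so this part is an improvement and not a departure from the protocol.

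What the objection does not answer is the narrowing of the laboratory shift tables against the protocol, and the absence of any baseline condition in the count.

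**Conclusion.** The point holds as a matter of dilution and noise. The SAP drops shift tables that the protocol plans for laboratory values generally, and its abnormality count cannot separate old from new for tests without one. With 20 per arm and assumed new onset of 30% against 5%, the chance that a harmful dose looks no worse than placebo is roughly doubled or more: 7% against 3% at 10% baseline prevalence, 16% against 6% at 30%, 21% against 8% at 40%. These figures rest on the assumed onset rates and on baseline abnormalities persisting. The documents give no prevalence for any test outside the liver enzymes.

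Two stronger readings are not supported. One is that pre-existing abnormalities overwhelm drug-induced ones throughout the safety data. At 10% prevalence they are 27% of the dose-arm count, and the planned table still shows 37.0% against 14.5%. The other is that the table is biased in favour of the drug. Under randomisation and the persistence assumption, pre-existing abnormalities add equally to each arm in expectation.

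**What to change.** **SAP 6.11.2**
- Define abnormality, and name the grading scale. The protocol uses CTCAE v3.0 for adverse events and DAIDS for toxicity management.
- Restore baseline-to-worst shift tables for all chemistry and haematology tests, as Protocol 13.4.3.2 states: by grade where one exists, otherwise low/normal/high.
- Count abnormalities that are new or worsened in grade from baseline, and show the number of subjects at risk. Worsening must be included, because a normal-to-abnormal rule shows nothing where nearly everyone starts abnormal.
- State a rule for missing baseline. SAP 6.2 already falls back to the last valid pre-dose value. For subjects without screening or post-baseline results, the protocol's rule is that they "will be excluded from the change from Baseline and shift table analyses"; say whether the count follows it.

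**SAP 6.11.3**
- Add a shift table from the last pre-dose ECG interpretation to the worst one on treatment, by arm.

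**Cost.** SAP wording and table programming, on data already collected. There will be more tables, and fewer than 20 at-risk subjects per arm for tests often abnormal at baseline.
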